### ***6.2. Secondary Endpoints***

Will be presented with descriptive statistics as above.

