## **20. Statistical methods**

### **20a Statistical methods for analysing primary and secondary outcomes**

The primary intention-to-treat analysis will investigate the between-group difference in ATRS. We will use a linear mixed effects regression model with the participant as random effect and time 13, 26 and 52 weeks, group allocation (standard care vs standard care plus add-on) and baseline value as fixed effects. Conclusions will only be drawn based on the primary endpoint (13 weeks).

All statistical analyses will be performed by a blinded data analyst according to a pre-established analysis plan. This plan is written in consultation with a statistician and will be published on the Aalborg University website before the inclusion of the last participant. STATA will be used as statistical software. We will use Q-Q plots and histograms to assess data normality.

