### 2.2. Secondary Objectives and Outcomes

The secondary objectives are to compare the secondary outcomes between standard care versus standard care combined with an early exercise program. In long-term follow-up to compare changes from 13 weeks follow-up to 26 and 52-weeks follow-up between groups. The objective outcomes are measured for injured and un-injured side and also presented as a side to side difference.

The outcomes are:

1. ATRS at 26- and 52 weeks

2. Physical Activity Questionnaire (IPAQ)(11) short form Danish version. It consists of 7 items concerning physical activity and gives an estimate of the total weekly physical activity measured in MET-minutes per week. The questionnaire will be filled out at 13-, 26- and 52-weeks follow-up.
3. Fear of re-rupture is measured by The Tampa scale of Kinesiophobia (TSK) (12). The questionnaire consists of 17 items concerning pain and kinesiophobia and has 4 answers from “Strongly disagree” to “Strongly agree” with a total range of 17 to 68 points. Four questions are reversed. Measured at baseline and at 9-, 13- and 52-weeks.
4. Fear of loading the Achilles tendon. Dichotomous Yes/no
  - a. During exercises. Measured at 9-weeks.
  - b. After weaning of the walking boot. Measured at 13 weeks
5. Percentage of the patients that can perform a one-legged heel-rise at 13- and 52 weeks.
6. Muscle endurance is measured with the MuscleLab measurement system (Ergotest Technology, Oslo, Norway)(13). Presented in Joules and repetitions.
  - a. Seated heel-rise test at 13 weeks\*. External weight load on the knee is calculated to 30% of the bodyweight.
  - b. One-legged standing heel-rise test at 52-weeks.
7. One-legged heel-rise height(13). Presented in centimeters.
8. Isometric muscle strength. Measured as maximal isometric plantar flexor muscle strength using Fysiometer(14). Position: seated with 90 degrees flexion in hip and knee. Measured at 9, 13, 52 weeks.
9. Achilles tendon resting angle (ATRA) is validated as an indirect measure of the Achilles tendon length (15).
10. Achilles tendon length in centimeters. Copenhagen Achilles length measure (CALM) using ultrasound(16). Performed at 9, 13 weeks and 52weeks.
11. Serious adverse events: Re-rupture, non-union, deep vein thrombosis (DVT).
12. Compliance with exercises. Number of sessions.

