13. Cost-effectiveness outcomes. Self-reported health state as measured by the EQ-5D-5L(17). Work productivity outcomes are measured using the Work Productivity and Activity Impairment Questionnaire WPAI:GH (18) and condition-related expenses as measured by a self-developed questionnaire. Measured at 9, 13, 26, 52 weeks.

\* Measures of strength endurance is different at the shortterm follow-up 13-weeks and 52-weeks as the standing one-legged heel-rise is not possible to perform for all patients in the early phase(13).

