### ***6.1. Primary Endpoint***

Descriptive statistics (mean (standard deviation) or median (interquartile range) for continuous variable or frequencies and proportions for categorical variables) will be used to describe demographics, for the two treatment groups individually and overall sample.

The primary intention-to-treat analysis will investigate the between-group difference in ATRS. We will use a linear mixed effects regression model with the participant as random effect and time 13, 26 and 52 weeks, group allocation (standard care vs standard care plus add-on) and baseline value as fixed effects. Conclusions will only be drawn based on the primary endpoint (13 weeks). We will use Q-Q plots and histograms to assess data normality.

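### SAP 2.2 sets between-arm comparison as the secondary objective, but SAP 6.2 plans only descriptive summaries, so 12 of the 13 listed items have no planned difference or interval

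*SAP*

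**What the plan says.** SAP 2.2 states a comparative aim: "The secondary objectives are to compare the secondary outcomes between standard care versus standard care combined with an early exercise program". It adds a longitudinal one: "In long-term follow-up to compare changes from 13 weeks follow-up to 26 and 52-weeks follow-up between groups". Thirteen numbered items follow. For the physical measures it says "The objective outcomes are measured for injured and un-injured side and also presented as a side to side difference".

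SAP 6.2 is a single sentence: "Will be presented with descriptive statistics as above". The reference back is to the first paragraph of SAP 6.1, which describes means with SDs, medians with interquartile ranges, or frequencies and proportions, for each arm and overall.

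The only between-arm model in either document is the ATRS mixed model in SAP 6.1, repeated in Protocol 20a. It has a random participant effect, with visit (13, 26, 52 weeks), "group allocation (standard care vs standard care plus add-on) and baseline value as fixed effects". Both sections restrict conclusions to week 13. Protocol 20a is headed "Statistical methods for analysing primary and secondary outcomes", but its text gives a method for ATRS alone. Protocol 20b lists no additional analyses.

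**The concern.** The objectives promise a comparison and the analysis section does not provide one. An analyst who follows SAP 6.2 literally produces columns of summaries by arm and leaves the stated objectives unanswered. An analyst who wants to answer them must choose the contrast, the model, the covariates and the interval method with the data in hand, which a pre-established plan is meant to prevent.

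The change objective is the more exposed of the two, because the planned summaries do not contain what is needed to put an interval on it. At stake is the secondary reporting, not the primary test.

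**Working it through.** **1. The plan's own figure.** Inputs from SAP 3.1: difference 10 points, SD 15, two-sided 5%, power 80%. The normal formula gives n = 2 × (1.960 + 0.842)² × (15/10)² = 35.3, so 36 per arm. The t-test version gives 36.3, so 37. The stated 37 per arm reproduces and is unaffected by this point. It is used below as the evaluable number.

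**2. Count of items.** The table sets the items in SAP 2.2 against every analysis in SAP 6.1–6.2 and Protocol 20a–20c.

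| Item | Between-arm contrast planned | Same measure at 13 weeks and later |
|---|---|---|
| 1 ATRS | partly (model in SAP 6.1) | 26 and 52 |
| 2 IPAQ | none | 26 and 52 |
| 3 TSK | none | 52 |
| 4 Fear of loading | none | no: different questions at 9 and 13 weeks |
| 5 Heel-rise ability | none | 52 |
| 6 Endurance | none | no: seated, then standing |
| 7 Heel-rise height | none | no visit stated |
| 8 Isometric strength | none | 52 |
| 9 ATRA | none | 52 (visits from Protocol 12) |
| 10 Tendon length | none | 52 |
| 11 Serious adverse events | none | event counts |
| 12 Compliance | none | no: journal ends at week 9 |
| 13 EQ-5D-5L, WPAI:GH, expenses | none | 26 and 52 |

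Items with no planned between-arm difference or interval: 13 − 1 = 12. Besides ATRS, seven items (2, 3, 5, 8, 9, 10, 13) repeat the same measure at 13 weeks and at least one later visit. Only IPAQ and item 13 do so at both 26 and 52 weeks.

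**3. Why ATRS is only partly covered.** With the listed terms, the expected score is a visit mean + β × group + γ × baseline. The between-arm difference is β at every visit, so the difference in change is β − β = 0 by construction. As an illustration, suppose true differences of 10, 5 and 0 points at the three visits, equal visit variances and complete data. The single group term then estimates (10 + 5 + 0)/3 = 5, which is not the difference at 26 or 52 weeks except by coincidence.

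**4. Interval for a difference in change.** Assume equal SDs at both visits and in both arms, and within-person correlation ρ.

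- Single-visit 95% half-width, 37 per arm: t(0.975, 72) × √(2/37) = 0.463 SD.
- The variance of a change is 2 × SD² × (1 − ρ), so the half-width for the difference in change is 0.463 × √(2(1 − ρ)).
- ρ = 0.2: 0.463 × √1.6 = 0.586 SD.
- ρ = 0.5: 0.463 × √1.0 = 0.463 SD.
- ρ = 0.8: 0.463 × √0.4 = 0.293 SD.

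The documents give no correlation, so these three values are assumptions. Identical by-arm means and SDs showing a 0.4 SD difference in change would fit an interval of 0.4 ± 0.586 (−0.19 to 0.99) at ρ = 0.2, or 0.4 ± 0.293 (0.11 to 0.69) at ρ = 0.8. The planned summaries cannot tell a reader which.

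**5. What the summaries do allow.** From mean, SD and n, or from counts, a reader can compute a crude single-visit difference and its interval. With complete data, subtracting by-arm means across visits gives the point estimate of a difference in change. Where only a median and interquartile range are reported, even the crude interval is not directly available.

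**The case against.** The strongest reply is that describing secondary outcomes is a legitimate choice, that the plan confines conclusions to 13-week ATRS, and that readers can reconstruct much of what is missing. Most of this stands. It is why the point is confined to secondary reporting. But the limit on conclusions governs inference; it does not withdraw the comparative objectives in SAP 2.2.

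It can also be said that SAP 6.2 does not forbid reporting the mean and SD of change by arm, which would make the interval recoverable. That is true, but no such summary is planned. Analyst blinding (Protocol 17a and 20a, SAP 3.2) reduces the risk from choosing methods late but does not remove it.

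Baseline adjustment is not something SAP 2.2 asks for, so its absence is not a contradiction. It appears in the fix because the plan already uses it for ATRS.

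Three stronger readings are tempting, and the documents do not support them:

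- A reader might infer that the primary conclusion is compromised by SAP 6.2. That section does not touch the primary analysis.
- A reader might infer that no between-arm information survives. Step 5 shows otherwise: for change, it is the interval that is lost.
- A reader might infer that the change objective reaches every item at both later visits. The visit schedule rules this out for most of them.

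In the other direction, a reader might leave compliance out of the count as naturally descriptive. The SAP makes no such exception.

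**Conclusion.** The mismatch is real and nothing elsewhere in the documents fills it. Twelve of the 13 items have no planned between-arm difference or interval, and ATRS at 26 and 52 weeks has only a pooled group effect. The change objective applies to ATRS and, if any later visit counts, to seven further items. None has an analysis that answers it.

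The loss that cannot be recovered from the planned summaries is the interval for a difference in change, whose half-width spans 0.29 to 0.59 SD over assumed correlations of 0.8 to 0.2. Those widths assume 37 evaluable per arm, equal SDs and continuous outcomes. The counts need no assumption beyond reading the visit lists as written.

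**What to change.** State which is intended and make SAP 2.2 and 6.2 agree.

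**If comparison is intended,** amend SAP 6.2 and label all of it exploratory:

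- **Continuous outcomes repeated with the same test:** between-arm difference with 95% CI at each visit, and difference in change from 13 weeks to each later measured visit. Use a mixed model with group, time, group-by-time, baseline where collected, and the stratification factors actually used. Protocol 16a gives sex while SAP 3.2 gives hospital and sex, so reconcile these first. Confirm whether WPAI:GH has a baseline: SAP 2.3 lists one, but the schedule in Protocol 13 does not clearly show it.
- **ATRS:** take the 26- and 52-week contrasts from a model with the same group-by-time term.
- **Physical measures:** name the dependent variable, for example the side-to-side difference. State the visit for heel-rise height.
- **Endurance:** because "Measures of strength endurance is different at the shortterm follow-up 13-weeks and 52-weeks", analyse the seated and standing tests as separate single-visit outcomes, with no change score.
- **Binary outcomes:** risk difference with a score-based 95% CI. For heel-rise ability, add a bootstrap interval for the difference in change from 13 to 52 weeks, resampling participants within arm.
- **Skewed outcomes:** fix the interval method now, for example a bootstrap for named outcomes such as IPAQ MET-minutes, instead of after viewing Q-Q plots.
- **Compliance:** label it descriptive, or give its contrast.
- **Costs:** specify the analysis, or say that it is reported separately.

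**If description only is intended,** change *compare* to *describe* in SAP 2.2 and delete the change objective.

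The second route costs wording only. The first adds modest analysis with no new data collection. Its downside is more exploratory intervals without multiplicity control, wide for rare events.

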### ***6.3. Major Protocol Deviations***

Any protocol deviations that happen during the course of the study will be registered.

#### **6.4. Missing data**

All data will be analyzed as intention to treat. In case of mis-diagnostics that is discovered after randomization, the participant will be excluded from the study.

#### **6.5. Exclusion cohort**

Will be reported descriptively.

### **7. Implementation of Analysis Plan**

This statistical analysis plan is a supplementary to the study protocol and will serve as a working document for the statistical analysis. All data is registered in REDCap and exported to a secure research file system at Aalborg University Hospital for analysis and storage.

